# 5.4 Dose Modifications

All toxicities should be graded according to the NCI Common Terminology Criteria for Adverse Events (CTCAE) version 4.0.

Version 4.0 of the CTCAE is identified and located on the CTEP website at (http://ctep.cancer.gov/protocolDevelopment/electronic\_applications/ctc.ht m. All appropriate treatment areas should have access to a copy of version 4.0 of CTCAE.

# 5.4.1 General Considerations

- a. A new cycle of treatment may begin when the ANC is ≥ 1,500/mcl, the platelet count is ≥ 75,000/mcl, and any treatment-related GI toxicity is resolved to ≤ Grade 1.
- b. If the initiation of a new cycle, or treatment during a cycle is delayed for ≥ 4 weeks, the patient should be removed from protocol treatment.
- c. Held doses are not to be made up.
- d. If one therapeutic agent is permanently discontinued secondary to toxicity, then therapy with the other study agents should continue and the patient should remain on-study with full adherence to all protocol-related requirements
- e. In the event of serious or life-threatening conditions, hold the offending agent. If the patient is to continue on therapy, all agents should be held until the toxicity resolves to grade < 2.

ARM	AGENT	INITIAL DOSE	LEVEL -1	LEVEL -2	
	Cetuximab	500 mg/m 	400 mg/m 	250 mg/m 	
A (IC)	Irinotecan	180 mg/m 	150 mg/m 	120 mg/m 	
B (ICR) Closed to accrual	Ramucirumab	8 mg/kg	6 mg/kg	5 mg/kg	
	Cetuximab	500 mg/m 	400 mg/m 	250 mg/m 	
	Irinotecan	180 mg/m 	150 mg/m 	120 mg/m 	
	Ramucirumab	6 mg/kg	5 mg/kg	4 mg/kg	
C (mICR)	Cetuximab	400 mg/m 	250 mg/m 	200 mg/m 	
	Irinotecan	150 mg/m 	120 mg/m 	90 mg/m 	

f. Dose reductions for all agents are as follows:

**NOTE:** In the event that an agent is given at dose level (-2) and dose modification rules call for further reduction, the agent should be discontinued.

Rev. 12/11, 6/14

# 5.4.2 Hematologic toxicities

No Ramucirumab or cetuximab dose modifications (or delays) will be made for hematologic toxicity. Continue Ramucirumab or cetuximab when irinotecan is held for hematologic toxicities.

Grade	Dose Modification				
2	Reduce irinotecan one dose level at the next cycle. For subsequent cycles, resume at the previous dose levels, provided ANC $\geq$ 1,500/mcl and platelets $\geq$ 75,000/mcl.				
3-4	Hold irinotecan. If counts recover to ANC $\geq$ 1,500/mcl and platelets $\geq$ 75,000/mcl, irinotecan may be resumed at one lower dose level at next cycle. For subsequent cycles, continue at the reduced dose levels from the previous cycle.				
Febrile neutropenia	Hold irinotecan. If fever resolves and counts recover to ANC $\geq$ 1,500/mcl and platelets $\geq$ 75,000/mcl, irinotecan may be resumed at one lower dose level at next cycle. For subsequent cycles, continue at the reduced dose levels from the previous cycle.				

# 5.4.3 Diarrhea

Rev. 6/14

Rev. 6/14

Rev. 6/14

No Ramucirumab dose delay will be made for diarrhea. Continue Ramucirumab when other agents are held. Dose modifications should be made for toxicity only when patient is receiving intensive loperamide therapy.

Grade	Dose Modification
2	Be sure intensive loperamide is being taken. For subsequent cycles, resume all agents at the previous dose levels, provided diarrhea has fully resolved before restarting treatment.
3	Be sure intensive loperamide is being taken. If so, and grade 3 diarrhea lasts longer than 48 hours, reduce irinotecan one dose level. Do not treat again until the diarrhea resolves to $\leq$ grade 2.
4	Be sure intensive loperamide is being taken. Hold irinotecan. If diarrhea resolves to ≤ grade 2, irinotecan and cetuximab should be resumed at one lower dose level for subsequent cycles. For subsequent cycles, continue both agents at the reduced dose levels from the previous cycle.

5.4.4 Nausea and/or vomiting

These dose modifications for nausea and/or vomiting should be made only if they persist/occur despite two treatments with adequate (combination) antiemetics therapy.

No Ramucirumab or cetuximab dose modifications (or delays) will be made for nausea/vomiting. Continue Ramucirumab or cetuximab when irinotecan is held.

Grade	Dose Modification
3-4	Reduce irinotecan one dose level. For subsequent cycles, continue irinotecan at the reduced dose level from the previous cycle.

Rev. 6/14

Rev. 6/14

5.4.5

Grade	Dose Modification
2	Reduce irinotecan one dose level for subsequent cycles. No modifications (or delays) will be made for Ramucirumab or cetuximab.
3	Hold irinotecan. If mucositis resolves to ≤ Grade 2, resume both irinotecan and cetuximab at one lower dose level for subsequent cycles. No modifications (or delays) will be made for Ramucirumab.
4	Hold ALL protocol treatment. If mucositis resolves to ≤ Grade 2, reduce all agents one dose level for all subsequent cycles.

#### 5.4.6 Pulmonary Toxicity

Mucositis

- 5.4.6.1 For Grade 2 or worsening pulmonary symptoms unrelated to underlying cancer, cetuximab treatment should be stopped and symptoms investigated. Cetuximab treatment may resume at one lower dose level when symptoms resolve to ≤ Grade 1 and cetuximab-related pneumonitis is ruled out.
- 5.4.6.2 For ≥ Grade 3 cough, dyspnea, hypoxia, pneumonitis, or pulmonary infiltrates, hold cetuximab until interstitial lung disease is ruled out. Continue Ramucirumab and irinotecan. Discontinue all protocol treatment if interstitial lung disease is confirmed.
- 5.4.7 Hypomagnesemia has been seen with cetuximab. For Grade 3-4 hypomagnesemia, hold cetuximab until hypomagnesemia resolves to ≤ Grade 2. Then restart cetuximab at the -1 dose. For any grade of hypomagnesemia, magnesium supplementation should be provided.

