### 5.2.2 Terminology

- Adverse Event (AE): Any untoward medical occurrence associated with the use of a drug in humans, whether or not considered drug related. Therefore, an AE can be ANY unfavorable and unintended sign (including an abnormal laboratory finding), symptom, or disease temporally associated with the use of a medicinal product, whether or not considered related to the medicinal product.
- **Attribution:** An assessment of the relationship between the adverse event and the protocol treatment, using the following categories.

ATTRIBUTION	DESCRIPTION
Unrelated	The AE is clearly NOT related to treatment
Unlikely	The AE is doubtfully related to treatment
Possible	The AE may be related to treatment
Probable	The AE is likely related to treatment
Definite	The AE is clearly related to treatment

- CAEPR (Comprehensive Adverse Events and Potential Risks List): An NCI generated list of reported and/or potential AEs associated with an agent currently under an NCI IND. Information contained in the CAEPR is compiled from the Investigator's Brochure, the Package Insert, as well as company safety reports.
- **CTCAE:** The NCI Common Terminology Criteria for Adverse Events provides a descriptive terminology that is to be utilized for AE reporting. A grade (severity) is provided for each AE term.
- Hospitalization (or prolongation of hospitalization): For AE reporting purposes, a hospitalization is defined as an inpatient hospital stay equal to or greater than 24 hours.
- Life Threatening Adverse Event: Any AE that places the subject at immediate risk of death from the AE as it occurred.
- Serious Adverse Event (SAE): Any adverse event occurring at any dose that results in ANY of the following outcomes:
  - Death

Rev. 6/14

- A life-threatening adverse event
- Inpatient hospitalization or prolongation of existing hospitalization (for ≥ 24 hours).
- A persistent or significant incapacity or substantial disruption of the ability to conduct normal life functions.
- A congenital anomaly/birth defect.
- Important Medical Events (IME) that may not result in death, be life threatening, or require hospitalization may be considered a serious adverse event when it may jeopardize the patient and may require medical or surgical intervention to prevent one of the outcomes listed in this definition.

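### For lung events unrelated to the cancer, Section 5.4.6.2 read literally lets cetuximab restart after Grade 3 or higher on looser terms than Section 5.4.6.1 sets after Grade 2

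*Combined protocol and SAP*

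**What the plan says.** **Section 5.4.6.1** gives the milder rule: "For Grade 2 or worsening pulmonary symptoms unrelated to underlying cancer, cetuximab treatment should be stopped and symptoms investigated". Its restart clause is explicit: "Cetuximab treatment may resume at one lower dose level when symptoms resolve to ≤ Grade 1 and cetuximab-related pneumonitis is ruled out".

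**Section 5.4.6.2** covers Grade 3 or higher cough, dyspnea, hypoxia, pneumonitis or infiltrates. The instruction is to "hold cetuximab until interstitial lung disease is ruled out. Continue Ramucirumab and irinotecan". If interstitial lung disease (ILD) is confirmed, all protocol treatment ends. It gives no recovery grade and no dose level, does not refer back to 5.4.6.1, and is not limited to events unrelated to the cancer.

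**Section 5.4.1** holds the general rules.
- Item a lets a new cycle begin on neutrophil recovery, once "the platelet count is ≥ 75,000/mcl, and any treatment-related GI toxicity is resolved to ≤ Grade 1".
- Item e states: "In the event of serious or life-threatening conditions, hold the offending agent". It goes on: "If the patient is to continue on therapy, all agents should be held until the toxicity resolves to grade < 2".
- The note under the dose table says that if an agent is at level -2 and "dose modification rules call for further reduction, the agent should be discontinued".

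**Section 5.2.2** defines a life-threatening event as "Any AE that places the subject at immediate risk of death from the AE as it occurred".

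**Section 5.4.17**, headed as covering other Grade 3 and 4 toxicities, holds the offending agents for Grade 3 until Grade 1 or less. It sends Grade 4 to the study chair and gives no restart dose.

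**The concern.** Dose-modification rules normally tighten as severity rises. Here the order appears reversed. A site following 5.4.6.2 to the letter could give an unreduced cetuximab dose to a patient whose dyspnea is still Grade 3, provided the ILD work-up is negative. A patient with a Grade 2 event would have to recover first and drop a dose level.

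Excluding ILD does not clear cetuximab. Its risk list in Section 5.3 includes dyspnea, cough and bronchospasm, and non-cardiogenic pulmonary edema as rare but serious. Section 8.1.2 also reports sporadic lung toxicity with irinotecan, one of the two agents that 5.4.6.2 continues.

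The stake is patient safety and consistency between sites. Section 1.6 records two toxic deaths on Arm B and presents stricter dose modification as part of the redesign. A severe-event rule that is looser than the moderate-event rule runs against that aim.

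**Working it through.** The plan gives no figure on this point, so there is none to reproduce. The check compares the rules and then does simple arithmetic on the dose table in 5.4.1, item f.

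**Step 1. Restart conditions for cetuximab.**

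| | 5.4.6.1 (Grade 2 or worsening) | 5.4.6.2 (Grade 3 or higher) |
|---|---|---|
| Limited to events unrelated to cancer | Yes | No |
| Recovery grade | Grade 1 or less | None stated |
| Exclusion | Cetuximab-related pneumonitis | ILD |
| Restart dose | One level lower | None stated |

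The two rules can be compared only where their populations overlap, that is, for events unrelated to the cancer. There 5.4.6.2 states one of the three conditions.

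**Step 2. Do the general rules in 5.4.1 fill the gap?** Item a tests neutrophils, platelets and treatment-related GI toxicity, not lung symptoms. Item e, where it applies, supplies a recovery grade (below 2) but no dose. Neither gives a restart dose.

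**Step 3. Size of the dose difference.** The ratio is the literal 5.4.6.2 dose divided by the dose after a one-level reduction.

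| Cetuximab level before the event | Arm A (500/400/250 mg/m²) | Arm C (400/250/200 mg/m²) |
|---|---|---|
| Initial | 500/400 = 1.25 (25% higher) | 400/250 = 1.60 (60% higher) |
| Level -1 | 400/250 = 1.60 (60% higher) | 250/200 = 1.25 (25% higher) |
| Level -2 | 250 against discontinue | 200 against discontinue |

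**Step 4. Grade 4 events.** Take Grade 4 as life-threatening in the sense of 5.2.2. If the patient is to stay on therapy, 5.4.1, item e, leaves no agent running until the toxicity is below Grade 2. Under 5.4.6.2 only cetuximab is held, so 1 of 2 agents continues on Arm A and 2 of 3 on Arm C. No sentence says which rule prevails.

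**Step 5. How many patients?** The documents give no rate for the subset where the rules diverge. The nearest figures are in the adverse event table of Section 8.2.10. With cetuximab plus irinotecan (n = 354), Grade 3-4 dyspnea was 2% and cough 0%; with cetuximab alone (n = 279), dyspnea was 7% and cough 1%. The revised study accrues 100 patients, about 50 per arm, so dyspnea at 2% to 7% gives 0.02 × 50 = 1 to 0.07 × 50 = 3.5 patients per arm. This indicates scale only. The table counts dyspnea reported as infusion reaction and does not separate out cancer-related cases. It omits hypoxia and infiltrates and has no ramucirumab data.

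**The case against.** **Cumulative reading.** The strongest reply is that 5.4.6.1 covers Grade 2 *or worsening* symptoms, which can naturally include Grade 3-4. It holds the section's only resume clause, and 5.4.6.2 never says that cetuximab may resume. On this view 5.4.6.2 simply adds an ILD work-up and a stop-all rule. The reading is sensible and would close the gap. But 5.4.6.2 is a separately numbered rule with its own trigger and its own end to the hold, and it has no cross-reference. A site could follow either reading in good faith.

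**Different scope.** 5.4.6.2 also catches tumor-related dyspnea or infiltrates, for which a diagnostic hold without a mandatory reduction is reasonable. This stands. A reader might infer that every Grade 3 or higher lung event lacks a needed reduction. The text supports that only for events unrelated to the cancer.

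**Fallback in 5.4.17.** If *other* in its heading reaches lung events, it supplies a recovery grade for Grade 3 and a study-chair discussion for Grade 4. Lung events have their own section, so its reach is arguable, and it still gives no dose.

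**Practice elsewhere.** Restarting without a numeric grade is not unique: 5.4.14 resumes at the current dose after a first Grade 3 rash that improves. On the other hand 5.4.7, directly after the lung rules, gives both a grade and a dose. The point therefore rests on 5.4.6.1 against 5.4.6.2, not on a uniform house style.

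**General against specific.** Organ-specific rules are often taken to govern over general ones. Sections 5.4.2, 5.4.3, 5.4.8 and 5.4.10.3 also continue agents in events that can be serious. So the conflict with 5.4.1, item e, is one case of a document-wide pattern. Extending it to all Grade 3 lung events would require reading *serious* as 5.2.2 defines it, which item e does not cite.

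**Other safeguards.** Confirmed ILD and symptomatic pulmonary embolism (5.4.9.3) stop all treatment. Grade 3-4 infusion reactions stop the offending agent (5.4.15). A delay of 4 weeks or more removes the patient (5.4.1, item b), and 5.6.1 requires stopping when the protocol's constraints harm the patient. These limit the harm but supply no restart dose once ILD is excluded.

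**Conclusion.** The point holds as a minor safety clarification. For lung events unrelated to the cancer, the stated rule after Grade 3 or higher has neither the recovery grade nor the dose reduction required after Grade 2. The literal restart dose is 25% to 60% above the reduced dose, or continuation instead of discontinuation at level -2. The Grade 4 conflict with 5.4.1, item e, is real in the text but secondary.

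This rests on a literal reading of 5.4.6.2, without carrying over 5.4.6.1 or 5.4.17, and on treating Grade 4 as life-threatening. The percentages are ratios from the dose table, not estimates of harm. Few patients should be affected, but no count is claimed for the diverging subset.

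Two stronger inferences should be resisted. A reader might conclude that the protocol intends full-dose rechallenge of unrecovered patients; it never says so, and only fails to rule it out. A reader might also suspect an effect on the PFS comparison. Nothing in the documents supports that, and power, type I error and event counts do not depend on this rule.

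**What to change.** **Main edit.** Add to 5.4.6.2 that, for events unrelated to underlying cancer, the 5.4.6.1 restart conditions also apply: symptoms Grade 1 or less, pneumonitis and ILD ruled out, one lower dose level.

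**Secondary edit, one of two.** Either limit the instruction to continue ramucirumab and irinotecan to events that are not life-threatening, or add one sentence to 5.4.1 saying whether item e overrides the organ-specific rules. The second option also settles the question for the other sections with the same pattern. Infusion reactions stay under 5.4.15 and symptomatic pulmonary embolism under 5.4.9.3.

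**Cost.** Addendum wording only, with no new visits, tests or patients. The clinical downside falls on a few patients whose event proves unrelated to the drug. From the initial dose the reduction is 500 to 400 mg/m² on Arm A (100/500 = 20%) and 400 to 250 mg/m² on Arm C (150/400 = 37.5%). At level -2 it means stopping cetuximab. If all agents are held for a Grade 4 event, the hold can last at most 28 - 1 = 27 days before 5.4.1, item b, removes the patient. With 14-day cycles that is up to two scheduled doses (days 0 and 14), which item e already implies.

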  - 5.4.12.2 For Grade 4 hemorrhage/bleeding, discontinue all protocol treatment.
- 5.4.13 Proteinuria (Dose delays for Ramucirumab only)
  - 5.4.13.1 For proteinuria  $\geq$  2+ or UPC (urinary protein: creatinine ratio) > 1.0: Confirm total urine protein with a 24-hour urine collection. For 2+ proteinuria, the scheduled dose of Ramucirumab may be given while awaiting the results of the 24-hour collection. For > 2+ proteinuria, hold Ramucirumab while awaiting results of the 24-hour urine collection. Other protocol treatment may be continued. If proteinuria is 2-3 g/24 hours, hold Ramucirumab until urine protein recovers to < 2 g/24 hours, then resume at the -1 dose level. Continue other protocol treatment. A second dose reduction (to 5 mg/kg every other week) is permitted if the protein level > 2g/24 hours recurs. Ramucirumab will be discontinued permanently if the protein level is > 3g/24hours, if there is a third occurrence of proteinuria > 2 g/24hours, or if the protein level does not return to < 2g/24hours within 2 weeks.
  - 5.4.13.2 If nephrotic syndrome (Grade 4 proteinuria) occurs, discontinue Ramucirumab.

Grade 3 Rash	Cetuximab	Outcome	Cetuximab Dose Modification
1st	Hold infusion	If improvement:	Continue at current dose
occurrence	1 to 2 wks	If no improvement:	Discontinue cetuximab
2nd	Hold infusion	If improvement:	Reduce one dose level
occurrence	1 to 2 wks	If no improvement:	Discontinue cetuximab
3rd	Hold infusion	If improvement:	Reduce two dose levels
occurrence 1 to 2 wks	If no improvement:	Discontinue cetuximab	
4th occurrence	Discontinue cetuximab		
Grade 4 Rash	Discontinue cetuximab		

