# 5.5.3 Antibiotics

Oral fluoroquinolone treatment should be initiated for any of the following:

- Diarrhea persisting for more than 24 hours despite loperamide
- ANC < 500/mcl (even in the absence of diarrhea or fever)
- Fever with diarrhea (even in the absence of neutropenia)
- Antibiotic therapy should also be initiated in patients who are hospitalized with prolonged diarrhea (even in the absence of neutropenia).
- 5.5.4 Lacrimation, rhinorrhea, miosis, diaphoresis, hot flashes, flushing, abdominal cramping, diarrhea, or other symptoms of early cholinergic syndrome may occur during or shortly after receiving irinotecan. Atropine, 0.25-1.0 mg IV or SC may be used to treat these symptoms. In patients with troublesome or recurrent symptoms, prophylactic administration of atropine shortly before irinotecan therapy may be considered. Additional antidiarrheal measures may be used at the discretion of the treating physician. Combination anticholinergic medications containing barbiturates or other agents (e.g., Donnatal®) should not be used because these may affect irinotecan metabolism. Anticholinergics should be used with caution in patients with potential contraindications (e.g., obstructive uropathy, glaucoma, tachycardia, etc.).

Rev. 6/14

[figure not shown]
Late diarrhea (e.g., developing more than 24 hours after irinotecan) should be managed with loperamide as described above.

- 5.5.5 Pegfilgrastim, epoetin and darbepoetin alfa may be administered at the treating investigator's discretion.
- 5.5.6 Dermatology Management

Suggested algorithm for management of cutaneous toxicity and paronychia:

In this protocol, acneiform rash and paronychia will be graded according to version 4.0 of the NCI-CTCAE definitions of rash/desquamation and nail changes. The patient should be followed until resolution of these toxicities.

Acneiform rash and paronychia should be managed according to the algorithms in Table 1-1 and Table 1-2. Cetuximab therapy treatment adjustments should be made according to Tables 1-3. Cetuximab dose reductions will be permanent (i.e., no dose re-escalations).

[figure not shown]

 STCN:
 Semisynthetic tetracyclines (doxycycline or minocycline)

 Topicals:
 Hydrocortisone 2.5% cream or alclomethasone 0.05% cream

 Oral Steroids:
 Methylprednisolone dose pack

Isotretinoin: Low doses (10-20 mg a day) or isotretinoin as a single agent

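### Section 5.4.7 restarts cetuximab after grade 3-4 hypomagnesemia at a fixed level, so a patient already at level -1 gets no reduction and a patient at -2 is restarted at a higher dose

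*Combined protocol and SAP*

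**What the plan says.** **Hypomagnesemia (5.4.7).** "For Grade 3-4 hypomagnesemia, hold cetuximab until hypomagnesemia resolves to ≤ Grade 2". The next sentence is "Then restart cetuximab at the -1 dose". There is no separate instruction for a patient already below the starting dose, or for a second episode.

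**Dose levels (5.4.1, item f, introduced by "Dose reductions for all agents are as follows").** Cetuximab at the starting dose, level -1 and level -2 is 500, 400 and 250 mg/m2 on Arm A (and on closed Arm B), and 400, 250 and 200 mg/m2 on Arm C. The note under the table reads: "In the event that an agent is given at dose level (-2) and dose modification rules call for further reduction, the agent should be discontinued".

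**Other cetuximab reductions.** Grade 4 diarrhea (5.4.3), grade 3 and grade 4 mucositis (5.4.5) and grade 2 or worsening pulmonary symptoms (5.4.6.1) each lower cetuximab by one level relative to where the patient is.

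**Permanence (5.5.6, Dermatology Management).** "Cetuximab dose reductions will be permanent (i.e., no dose re-escalations".

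**Grade 3 rash with improvement (5.4.14).** First occurrence: "Continue at current dose". Second: "Reduce one dose level". Third: "Reduce two dose levels". A fourth occurrence, or any grade 4 rash, ends cetuximab.

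**The concern.** A dose-modification rule for a grade 3-4 toxicity would be expected to lower the dose or stop the drug. Because 5.4.7 names a level and not a step, its effect depends on where the patient already is. It is a reduction from the starting dose, no change from -1, and an increase from -2. In the last case a site cannot follow both 5.4.7 and the permanence sentence in 5.5.6, if that sentence covers all cetuximab reductions.

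Patient safety is the first thing at stake, because the dose could rise straight after a severe toxicity. Consistency between sites is the second. Section 1.6 explains that the trial was redesigned because of toxicity and was to apply stricter dose modification. A rule that can leave the dose unchanged or raise it works against that aim. Toxicity is also a secondary endpoint in section 9.1, and sites that read the rule differently would add avoidable variation to it.

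**Working it through.** The plan gives no figure to reproduce here. The check applies 5.4.7 to each possible current level.

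**Inputs.** Dose levels from the table in 5.4.1; the restart rule from 5.4.7.

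**Formula.** Change = (dose at level -1) / (current dose) - 1.

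| Arm | Current level | Current dose (mg/m2) | Restart dose under 5.4.7 (mg/m2) | Change |
|---|---|---|---|---|
| A | start | 500 | 400 | 400/500 - 1 = -20% |
| A | -1 | 400 | 400 | 400/400 - 1 = 0% |
| A | -2 | 250 | 400 | 400/250 - 1 = +60% |
| C | start | 400 | 250 | 250/400 - 1 = -37.5% |
| C | -1 | 250 | 250 | 250/250 - 1 = 0% |
| C | -2 | 200 | 250 | 250/200 - 1 = +25% |

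If 5.4.7 were read as one step down from the current level, a patient at -1 would go to 250 (Arm A) or 200 (Arm C), and a patient at -2 would stop cetuximab under the note in 5.4.1. The two readings therefore agree only for a patient still at the starting dose.

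**Can a patient be at -1 or -2 beforehand?** Yes. One of the events listed in 5.4.3, 5.4.5 or 5.4.6.1 gives -1, and two give -2. A first hypomagnesemia episode also gives -1, and a second then restarts at the same dose. Magnesium is tested every 2 weeks (section 7), so a recurrence would be seen.

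**Rash table, rash-only course.** The first occurrence leaves the patient at the starting level and the second gives -1. For the third there are two readings:

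- Counted from the starting level: 0 - 2 = level -2, which is 250 mg/m2 on Arm A and 200 mg/m2 on Arm C.
- Counted from the current level: -1 - 2 = -3, a level that does not exist. Extending the note in 5.4.1 to this case would mean stopping cetuximab, and the fourth-occurrence row would then never be used in such a course.

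On the current-level reading no row raises a dose, from any starting point or in any arm.

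**The case against.** The strongest reply is that the problem is narrow. A rise needs level -2, typically two earlier cetuximab-reducing events, and then grade 3-4 hypomagnesemia. Grade 3 diarrhea lowers irinotecan only. The documents give no frequency for this sequence. That stands, and it limits the size of the point. It does not touch the case at -1, where one earlier event or a recurrent episode is enough.

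A second reply is that the permanence sentence belongs to dermatology. If it covers skin toxicity only, it does not conflict with 5.4.7. If it is general, it already forbids the rise. Its scope is open, but either way the text needs repair: the first reading leaves the rise unopposed, and the second leaves two instructions that cannot both be followed.

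Several stronger conclusions are tempting, and the documents do not support them:

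- *The rash table also raises the dose.* A reader could get a rise only by counting the second-occurrence reduction from the starting dose in a patient already at -2 for another toxicity. That contradicts the instruction to reduce, and the first row refers to the current dose.
- *The rash table is unworkable.* Counted from the starting level it is coherent: no change, -1, -2, stop. The tables cited in 5.5.6 are not visible in the text available and may settle the reference level.
- *Section 5.4.7 directly contradicts the level -2 note.* The note applies when a further reduction is called for. Read literally, 5.4.7 calls for none at -2, so the note is not triggered. Read as a step down, the note gives a clear answer and the dose does not rise.
- *Patients at low levels will be common, because 15 of 16 Arm B patients needed reduction.* That figure in section 1.6 is not specific to cetuximab and comes from the closed arm at its higher starting doses. On Arm A it was 3 of 17, with mean cetuximab dose intensity of 98%.
- *The comparison of Arm C with Arm A is distorted.* The primary comparison is PFS, and dose intensity is not an endpoint. The early grade 3 or higher test sets Arm C against a fixed 16.7%, and the safety evaluation follows patients through 2 cycles. If each event lowers cetuximab by one level at a cycle boundary, -2 is first reached at cycle 3, outside that window.

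**Conclusion.** The point holds for hypomagnesemia. As written, 5.4.7 gives no reduction at level -1 and an increase at -2, of 60% on Arm A and 25% on Arm C. The increase conflicts with the permanence sentence in 5.5.6 if that sentence is general, as its wording suggests. These percentages rest only on the 5.4.1 table and a literal reading of 5.4.7. How many patients would be affected cannot be estimated from the documents, and no effect on the efficacy or toxicity comparison has been shown.

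For rash the conclusion is weaker. The visible text leaves the reference level of the third-occurrence reduction unstated, with either level -2 or a step past the end of the table as the result. This is subject to what the tables cited in 5.5.6 contain.

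This is a safety-relevant inconsistency worth correcting because the correction is cheap. It does not undermine the design.

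**What to change.** In the next addendum, reconcile 5.4.7 with the level table and note in 5.4.1 and with 5.5.6:

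1. State in 5.4.7 whether the restart level is fixed or counted from the current level, and what applies to a patient already at -1 or at -2, including after an earlier hypomagnesemia episode.
2. State whether the permanence sentence in 5.5.6 covers all cetuximab reductions or only those for skin toxicity. If all, move it to 5.4.1.
3. State in 5.4.14 whether the one-level and two-level reductions count from the starting or the current level, and check this against the tables cited in 5.5.6.

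Which rule to adopt is a clinical decision for the investigators, and none is proposed here. The cost is a few sentences of protocol text and notice to sites. Sample size, data collection and analysis do not change.
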